9.5.1. Case report forms (CRFs)/Data collection tools (DCTs)/Electronic data record

As used in this protocol, the term CRF should be understood to refer to electronic data record.

A CRF is required and should be completed for each included patient. The completed original CRFs are the sole property of Pfizer and should not be made available in any form to third parties, except for authorized representatives of Pfizer or appropriate regulatory authorities, without written permission from Pfizer. The investigator shall ensure that the CRFs are securely stored at the study site in encrypted electronic form and will be password protected to prevent access by unauthorized third parties.

The investigator has ultimate responsibility for the collection and reporting of all clinical, safety, and laboratory data entered on the CRFs and any other data collection forms (source documents) and ensuring that they are accurate, authentic/original, attributable, complete, consistent, legible, timely (contemporaneous), enduring, and available when required. The CRFs must be signed by the investigator or by an authorized staff member to attest that the data contained on the CRFs are true. Any corrections to entries made in the CRFs or source documents must be dated, initialed, and explained (if necessary) and should not obscure the original entry.

The source documents are the hospital or the physician's chart. In these cases, data collected on the CRFs must match those charts.

9.5.2. Record retention

To enable evaluations and/or inspections/audits from regulatory authorities or Pfizer, the investigator agrees to keep records, copies of all CRFs, safety reporting forms, and adequate documentation of relevant correspondence (e.g., letters, meeting minutes, and telephone call reports). The records should be retained by the investigator according to local regulations or as specified in the clinical study agreement (CSA), whichever is longer. The investigator must ensure that the records continue to be stored securely for so long as they are retained.

If the investigator becomes unable for any reason to continue to retain study records for the required period (e.g., retirement, relocation), Pfizer should be prospectively notified. The study records must be transferred to a designee acceptable to Pfizer, such as another investigator, another institution, or to an independent third party arranged by Pfizer.

Study records must be kept for a minimum of 15 years after completion or discontinuation of the study, unless *GermanOncology* or as required by applicable local regulations.

The investigator must obtain Pfizer's written permission before disposing of any records, even if retention requirements have been met.

9.6. Data analysis

The data analysis are carried out for all evaluable patients for whom the inclusion criteria are met, first-line therapy with at least 1 application has been documented and no exclusion criteria exist.

Detailed methodology for summary and statistical analyses of data collected in this study will be documented in a statistical analysis plan (SAP), which will be dated, filed and maintained by the sponsor. The SAP may modify the plans outlined in the protocol; any major modifications of primary endpoint definitions or their analyses would be reflected in a protocol amendment.

9.7. Quality control

The most relevant step in quality control and quality assurance will be an avoidance of inaccuracies or mismatches in terminology by data entries in data fields over a selection of parameters or descriptions out of pre-defined drop-down-lists. Free text is only intended for descriptions after selection of "other", which will be possible in some data fields, where a pre-definition cannot be

implemented for 100%. For all dates regarding parameters like first diagnosis, pre-treatments, therapy administrations automatic checks are implemented for data entries, so that the course of treatment will be shown correctly (e.g. adjuvant therapy after OP and before palliative therapy, end of 1L before start of 2L, end of therapy after last administration). In defined data fields new explanation fields will open up after selection of specific documentations (e.g. after selection of dose modification query for modified dose, after selection of end of therapy query for reason). In data fields with information like weight, height or age, automatic standard range checks, are implemented to avoid input errors. In addition to these automatic checks every data entry will also be checked by an experienced data manager and, if needed, by the medical lead.

In case of relevant inaccuracy or implausibility, patient's data files will be rejected before further analytical processes will start. After the decision for rejection of patients the investigator will be informed about the reason for rejection and all data will be deleted immediately.

9.8. Limitations of the research methods

For this data project only data out of the medical records of patients, who are treated under daily routine in oncological institutions like practices or hospitals will be used and these data of investigations or visits have to be generated under standard conditions. The documentation in the eCRF and so also the analyses are dependent on the availability of the data in the medical records. Such availability should be given for most of the mandatory data fields, as these will be standard facts during oncological treatments. If data are not available, this has to be documented explicitly. In case of a high amount of missing data, a patient can be rejected by the data manager or medical lead, as otherwise no representative analyses can be performed.

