8.2. Study Objectives

To answer these questions the following objectives are derived:

Primary Objective(s):

- Progression-free survival (PFS) for 1L therapies, expressed as median and as rates at timepoints of 6, 9, 12 and 18 months after start of 1L

Secondary Objectives:

- Overall survival (OS) of 1L therapies, expressed as median and rates at timepoints of 12 and 18 months after start of 1L therapy
- Best response in 1L overall and in dependence of administered drug regimen
- Progression-free survival of 1L therapies in dependence of specific drug regimen
- Pre- and post-treatments (i.e. surgery, radiotherapy, medicinal therapies) before/after TKI + ICI and ICI + ICI in 1L
- Duration of response (DoR) in 1L overall and in dependence of administered drug regimen (TKI + ICI or ICI + ICI)
- Frequency of dose modifications and temporary/permanent discontinuations of 1L therapies and their reasons
- Proportions of modifications by dose reduction compared to cancelling single applications
- Effectiveness (PFS, OS and best response) of administered 1L therapies under real world conditions by medical specialty (urology, medical oncology) and setting (practice, hospital)

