Supportive drugs prescribed during 1L	Relevant for outcomes	Medical Chart	Administered supportive drugs in connection with cancer therapy
Date of first response and best response in 1L incl. date and mode of assessment	Relevant for outcomes	Medical Chart	dd/mm/yyyy; CT/MRI/ultrasound/x-ray; clinical assessment; laboratory
Assessment of first and best response in 1L	Relevant for outcomes	Medical Chart	CR/PR/SD/PD/ND
Date of tumor progression	Relevant for outcomes	Medical Chart	dd/mm/yyyy
Reasons for end of 1L	Relevant for outcomes	Medical Chart	Progression; intolerance; decision oncologist; patient's wish; death; deterioration performance
Subsequent therapies (Second-line therapy (2L) and higher) with drugs/protocol and dates for start / end	Relevant for outcomes	Medical Chart	y/n; used drugs/regime; start/stop
Concomitant diseases and therapeutic measures	Relevant for outcomes	Medical Chart	Detailed diagnosis; therapeutic measures OP/medicinal/none/other

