9.4. Study size

Based on public data the population of patients with aRCC and an indication for a 1L therapy is around $n = 4.500 - 5.000$ patients per year ([Robert Koch Institute 2020](#)). In the period of 01 January 2020 – 31 December 2021, which is the main period of interest in the study for completing or starting 1L therapies, the total population of patients with aRCC would be around $n = 9.000 - 10.000$ patients. To estimate the needed number of patients in the study to reach adequate representation across Germany, the following common formula is used

$$n = \frac{z^2 \pi(1 - \pi)N}{z^2 \pi(1 - \pi) + E^2(N - 1)}$$

N = population of patients with aRCC and indication for 1L = 10.000 patients in 24 months

$\Pi = 0,5$ (consensus, if attribute is unknown before study)

E = margin of error = 5% = 0,05

$Z = 1,96$ (for confidence interval of 95%)

Based on these assumptions (PFS of 1L therapies included in guidelines was 8.4 – 151 months in clinical studies) the number of patients needed for representative statement regarding the primary objective (= PFS rates at defined time points under real world conditions) is at least $n = 370$. With a buffer of around 10% the sample size in the study should be $n = 400$ patients with aRCC and 1L therapies in the period from 01 January 2020 – 31 December 2021. Based on published data for PFS it could be assumed for part 2, that also the number of patients with combination therapies in part 2 ($n = 300$) will grant a representative statement to all research questions. Based on information of urological and oncological experts as well as own data of the GermanOncology *¹ network (see below), the following assumptions could be set:

- Number of patients with new 1L in urological practices (per practice 1- 3 urologists) = 4 - 6 per year
 - Number of patients with new 1L in period of 24 months = 8 - 12
- Number of patients with new 1L in oncological practices (per practice 2- 4 oncologists) = 4 - 6 per year
 - Number of patients with new 1L in period of 24 months = 8 - 12
- Number of patients with new 1L in hospitals with urological focus = 8 - 12 per year
 - Number of patients with new 1L in period of 24 months = 16 – 24
- Proportion of 1L therapies in urological and oncological practices: 50% : 50%
- Proportion of patients treated with 1L in practices and hospitals (as most of therapies are oral therapies): 65% : 35%

Based on the assumptions the needed number of sites are at least:

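### PFS by regimen, specialty and setting rests on unscheduled routine assessments, and the last progression-free assessment before progression is not collected, so unequal assessment intervals could be only partly told apart from a PFS difference

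*Combined protocol and SAP*

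**What the plan says.** PFS is the primary outcome, reported as a median and as rates at 6, 9, 12 and 18 months. Two secondary objectives in section 8.2 break it down by group: "Progression-free survival of 1L therapies in dependence of specific drug regimen", and effectiveness including PFS "under real world conditions by medical specialty (urology, medical oncology) and setting (practice, hospital". The abstract's data analysis entry lists urology versus medical oncology and practices versus hospitals as subgroups.

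Section 9.8 states that "these data of investigations or visits have to be generated under standard conditions", and section 10 adds that no extra investigations were done. The only limitation discussed in 9.8 is whether data are available in the chart; assessment timing is not mentioned.

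Tab. 2 (section 9.2) is introduced as the list needed for all outcomes. Its tumour assessment dates are those of first response and best response, and "Date of tumor progression". It has no list of assessment dates, no imaging interval and no date of the last assessment without progression.

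Section 9.3 rules out data queries because the records are fully anonymised. Section 9.6 leaves detailed methods to a separate SAP.

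**The concern.** Progression is dated when it is found. On average, a group assessed less often has progression recorded later, even when the disease behaves identically. The distortion can be examined only if one knows, for each patient who progressed, when the tumour was last seen without progression. Tab. 2 does not supply that date, and a later SAP cannot analyse a date that was never captured.

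At stake are the by-group PFS results, which section 8.2 labels effectiveness. A difference between urology and oncology, practice and hospital, or two regimens could arise partly from different assessment intervals, and the collected data would give little means of recognising it. OS is not affected.

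**Working it through.** **1. The plan's own figure.** Section 9.4 uses "N = population of patients with aRCC and indication for 1L = 10.000 patients in 24 months", a proportion of 0.5, a 5% margin and z = 1.96.

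n = 1.96² × 0.25 × 10,000 / (1.96² × 0.25 + 0.05² × 9,999) = 9,604 / 25.9579 = 369.98, so 370.

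The figure reproduces. It is the precision of one proportion in the whole cohort and says nothing about differences between groups or about assessment timing.

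**2. Assumptions for the size.** The documents give no imaging interval; 2, 3, 4 and 6 months are assumed. PFS is taken as exponential, S(t) = 2^(−t/m), identical in the groups compared, with m = 12 months or m = 8.4 months. Both lie in the abstract's range of 8.4 to 15.1 months (section 9.4 prints the upper end as 151, evidently a lost decimal point).

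**3. Mechanism with perfectly regular scans.** With a scan every D months, the recorded rate at t is S at the last scan not later than t. For m = 12:

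| Month | 2-monthly | 4-monthly | Gap (points) |
|---|---|---|---|
| 6 | S(6) = 70.7% | S(4) = 79.4% | 8.7 |
| 9 | S(8) = 63.0% | S(8) = 63.0% | 0 |
| 12 | S(12) = 50.0% | S(12) = 50.0% | 0 |
| 18 | S(18) = 35.4% | S(16) = 39.7% | 4.3 |

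The gap depends on where the time point falls between scans. Routine scans are not this regular, so these extremes are not used for the conclusion.

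**4. Irregular scans.** Simulation with 400,000 draws per case, gaps between scans varying with SD 0.5 month, and progression dated at the first scan after onset. At m = 12 the observed 6-month rate is 75.4%, 77.8% and 79.4% for 2-, 3- and 4-monthly imaging, against a true 70.7%. The gap between 4- and 2-monthly imaging is:

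| True median | 6 mo | 9 mo | 12 mo | 18 mo | Observed medians |
|---|---|---|---|---|---|
| 12 months | 4.0 | 1.1 | 3.5 | 2.1 | 13.1 vs 14.1 |
| 8.4 months | 5.0 | 1.6 | 3.9 | 2.1 | 9.5 vs 11.0 |

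Repeat runs move these by up to about 0.3 points and 0.2 month. At 9 months with m = 12, 4-monthly imaging gives a lower rate than 3-monthly (64.3% versus 65.3%), so the direction is not uniform across time points.

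**5. Deaths.** PFS counts death from any cause, and a death date does not depend on imaging. If 15% of events are deaths (assumed), the 6-month gap falls to about 3.5 points (m = 12) and 4.3 points (m = 8.4).

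**6. Would the missing date help?** A second simulation used 200 patients per group, 300 repeats per case, true medians of 8.4, 12 and 15.1 months, 15% deaths, follow-up of 12 to 36 months and identical true PFS. The true hazard ratio (less versus more frequent imaging) is therefore 1.

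| Intervals (months) | Recorded progression date (Cox) | Interval-censored, best-response date as lower limit | Interval-censored, last progression-free date as lower limit |
|---|---|---|---|
| 3 vs 4 | 0.95–0.98 | 0.95–0.98 | 1.00–1.02 |
| 2 vs 4 | 0.91–0.95 | 0.88–0.93 | 0.99–1.01 |
| 3 vs 6 | 0.88–0.91 | 0.90–0.94 | 1.00–1.01 |

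The last column is a best case: the fitted model was the true one, and patients without an event were censored at their last assessment. Censoring them at the end of follow-up instead gives 0.96 to 0.99 across the three contrasts, so most of the distortion is still removed. A nominal 5% Cox test on the recorded date rejects in about 3 to 7% of repeats for 3 versus 4 months, 7 to 13% for 2 versus 4, and 10 to 23% for 3 versus 6.

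**The case against.** The strongest objection is that nothing in the documents says urologists, oncologists, hospitals or regimens differ in assessment interval. If the intervals are similar, the problem disappears. That stands: unequal imaging is possible, not shown. But without the extra date it could hardly be checked either.

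Second, the effect is modest. With 400 patients split 65:35, i.e. 260 and 140, the 95% half-width for a difference in rates near 77% is 1.96 × √(0.77 × 0.23 × (1/260 + 1/140)) = 8.6 points before censoring. An artefact of 4 points is about half of that, and for 3- versus 4-monthly imaging the test size is barely affected. This also stands and limits the importance of the point. It does not remove it, because the distortion is systematic and shifts reported medians and rates without warning.

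Third, the first- and best-response dates already give a lower bound. They do, in part, so a reader who concludes that the artefact is wholly inseparable goes too far. In the simulation, however, that bound did not remove the distortion.

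Fourth, no test or model is stated for the by-group results, and methods are deferred to the SAP. That is true, but descriptive estimates carry the same distortion.

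**Conclusion.** The point holds in a limited form. The missing field is a matter of record in Tab. 2; the size depends on assumed intervals. Under 2- versus 4-monthly imaging the artefact is about 4, 1, 3 to 4 and 2 points at the four time points and about 1 month in the median (true median 12 months), or about 5, 1.5, 4 and 2 points and 1.5 months (true median 8.4 months). It is smaller when deaths are counted, and at single time points the direction can reverse between 3- and 4-monthly imaging.

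Three stronger readings are tempting and not supported:
- A reader might infer that the by-group PFS results will be biased. The documents do not show that intervals differ.
- A reader might set 4 to 5 points against the 5% margin in section 9.4. That margin concerns one whole-cohort proportion, and 4 to 5 points is the 6-month figure, the largest of the four.
- A reader might infer that a difference surviving an interval-censored analysis can be read as a difference in effectiveness. The groups are not randomised and the protocol states no confounder adjustment, so it cannot.

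The change is worth making because it is cheap and cannot be made later.

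**What to change.** - Before data collection starts, add one field to Tab. 2 and the eCRF, for progressed patients only: the date of the last tumour assessment without progression before the date of tumor progression.
- Keep Kaplan-Meier on the documented progression date as the main analysis.
- For each PFS table by regimen, specialty or setting, report the median interval between the two dates per group. Add an interval-censored PFS estimate (Turnbull or Weibull) as a sensitivity analysis, with deaths without progression entered as exactly dated events.
- State in section 9.8 that assessment timing was not standardised, and that by-group PFS differences are descriptive and must be read alongside these two results. Do not make interpretation conditional on a difference persisting in the sensitivity analysis: that rule has no criterion and ignores confounding.

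The cost is one chart date per progressed patient, one extra analysis per by-group table and slightly more abstraction time.

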9.9. Other aspects

Not applicable.

10. PROTECTION OF HUMAN SUBJECTS

As only fully anonymized data of patients will be used in the project, all requirements for data protection in accordance to the national and EU General Data Protection Regulations are fully preserved. The data will be captured retrospectively, so that all patients were already treated under standard daily conditions without any kind of additional investigations or other interventions.

10.1. Patient information

All parties will comply with all applicable laws, including laws regarding the implementation of organizational and technical measures to ensure protection of documented patient data. Such measures will include omitting patient names or other directly identifiable data in any reports, publications, or other disclosures, except where required by applicable laws.

The documented patient data will be stored at the study site in encrypted electronic form and will be password protected to ensure that only authorized study staff have access. The study site will implement appropriate technical and organizational measures to ensure that the documented patient

data can be recovered in the event of disaster. In the event of a potential documented patient data breach, the study site shall be responsible for determining whether a documented patient data breach has in fact occurred and, if so, providing breach notifications as required by law.

To protect the rights and freedoms of natural persons with regard to the processing of documented patient data, when study data are compiled for transfer to Pfizer and other authorized parties, patient names will be removed and will be replaced by a single, specific, numerical code, based on a numbering system defined by Pfizer. All other identifiable data transferred to Pfizer or other authorized parties will be identified by this single, patient-specific code. In case of data transfer, Pfizer will maintain high standards of confidentiality and protection of patients' documented data consistent with the clinical study agreement and applicable privacy laws.

10.2. Patient consent

As this study does not involve data subject to privacy laws according to applicable legal requirements, obtaining informed consent from patients by Pfizer should not be required.

10.3. Institutional review board (IRB)/Independent ethics committee (IEC)

There must be prospective official statement or approval of the study protocol, protocol amendments, and other relevant documents (e.g., informed consent forms if applicable) from the relevant IRBs/IECs. All correspondence with the IRB/IEC must be retained. Copies of IRB/IEC approvals must be forwarded to Pfizer.

10.4. Ethical conduct of the study

The study will be conducted in accordance with legal and regulatory requirements, as well as with scientific purpose, value and rigor and follow generally accepted research practices described in policies for Good Clinical Practice (GCP), Good Epidemiological Practice (GEP), Good Pharmacovigilance Practice (GVP) and the Declaration of Helsinki by the World Medical Association.

11. MANAGEMENT AND REPORTING OF ADVERSE EVENTS/ADVERSE REACTIONS

This study protocol requires human review of patient-level unstructured data; unstructured data refer to verbatim medical data, including text-based descriptions and visual depictions of medical information, such as medical records, images of physician notes, neurological scans, x-rays, or narrative fields in a database. The reviewer is obligated to report adverse events (AEs) with explicit attribution to any Pfizer drug that appear in the reviewed information (defined per the patient population and study period specified in the protocol). Explicit attribution is not inferred by a temporal relationship between drug administration and an AE but must be based on a definite statement of causality by a healthcare provider linking drug administration to the AE.

The requirements for reporting safety events on the non-interventional study (NIS) adverse event monitoring (AEM) Report Form to Pfizer Safety are as follows:

- All serious and non-serious AEs with explicit attribution to **any Pfizer drug** that appear in the reviewed information must be recorded and reported, within 24 hours of awareness, to Pfizer Safety using the NIS AEM Report Form.
- Scenarios involving drug exposure, including exposure during pregnancy, exposure during breast feeding, medication error, overdose, misuse, extravasation, lack of efficacy, and occupational exposure associated with the use of a Pfizer product must be reported, within 24 hours of awareness, to Pfizer Safety using the NIS AEM Report Form.
- For exposure during pregnancy in studies of pregnant women, data on the exposure to avelumab, axitinib, or sunitinib, during pregnancy, are not reportable unless associated with serious or non-serious adverse events.
- For these AEs with an explicit attribution or scenarios involving exposure to a Pfizer product, the safety information identified in the unstructured data reviewed is captured in the Event Narrative section of the report form, and constitutes all clinical information known regarding these AEs. No follow-up on related AEs will be conducted.

All the demographic fields on the NIS AEM Report Form may not necessarily be completed, as the form designates, since not all elements will be available due to privacy concerns with the use of secondary data sources. While not all demographic fields will be completed, at the very least, at least one patient identifier (e.g., gender, age as captured in the narrative field of the form) will be reported on the NIS AEM Report Form, thus allowing the report to be considered a valid one in accordance with pharmacovigilance legislation. All identifiers will be limited to generalities, such as the statement “A 35-year-old female...” or “An elderly male...” Other identifiers will have been removed.

Additionally, the onset/start dates and stop dates for “Illness,” “Study Drug,” and “Drug Name” may be documented in month/year (mmm/yyyy) format rather than identifying the actual date of occurrence within the month /year of occurrence in the day/month/year (DD/MMM/YYYY) format.”>

All research staff members must complete the following Pfizer training requirements:

- *“Your Reporting Responsibilities (YRR) Training for Vendors.”*

These trainings must be completed by research staff members prior to the start of data collection. All trainings include a “Confirmation of Training Certificate” (for signature by the trainee) as a record of completion of the training, which must be kept in a retrievable format. Copies of all signed training certificates must be provided to Pfizer.

|Re-training must be completed on an annual basis using the most current Your Reporting Responsibilities training materials.

